8.1 Primary Endpoint: Long Term Efficacy – 12 months

The primary outcome of the study will be survival without CRM through 12 months CGA as measured by a validated respiratory diary based scoring system (presence of wheezing and/or coughing 2 days per week for 3 consecutive weeks) and pulmonary questionnaires (decrease in respiratory illness requiring medications, unscheduled medical visits and/or ER or hospital admissions) which have been shown to correlate closely with abnormalities on pulmonary function testing. The 12 month CGA endpoint has been shown to be more predictive of respiratory morbidity at two years of life than a diagnosis of BPD at 36 weeks CGA in previous studies of high frequency oscillatory ventilation in preterm infants.

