Power Analysis: A total of 88 preterm infants will be randomized to placebo, lower dose, or higher dose rhCC10 with an allocation ratio of 2:1:1. The primary analysis will be the comparison of placebo versus both rhCC10 dose groups combined. The prior trial demonstrated that the two doses are likely to yield similar results. Two doses will be used for the purpose of extending the safety profile for each individual dose, as that safety data may facilitate the choice of dose for a future Phase III confirmatory study. For SAEs or AEs with background rates of 5%, 10%, or 15%, the sample size of 22 in either dosing group will provide a probability of observing it of 68%, 90%, and 97%, respectively. The proposed trial is powered for the comparison of the two doses combined versus placebo for the composite endpoint of death or development of CRM. Secondarily, the study will yield effect size estimates for each individual dose versus placebo. Our assumptions regarding the comparison of placebo versus rhCC10 are based on the previous study with 7 placebo, 8 lower dose, and 7 higher dose infants (one infant in each of the rhCC10 treatment groups died). It is important to address the combined endpoint of death or re-admission to the hospital for respiratory problems. In the previous study, one loss-to-follow-up occurred in each of the three experimental groups and one death occurred in each of the rhCC10 groups. At 6 months, 3 of the 6 infants on placebo with follow-up were re-admitted to the hospital for respiratory problems and none of the 11 subjects treated with either rhCC10 dose with follow-up data were re-hospitalized. A realistic and conservative assumption for the 3 lost-to-follow-up babies is that they all either died or had respiratory disease. Then the proportions with disease or death on placebo and rhCC10 are assumed to have been 0.57 and 0.27. If the proportions in the proposed study are similar, with 44 subjects on placebo and 44 subjects in the two dose groups combined, power will be 82% with $\alpha=0.05$. nQuery Advisor version 6 was used.

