Data will be summarized for the total cases and by treatment group with respect to: 1) baseline demographic and clinical characteristics and 2) efficacy and safety observations and measurements. Analyses will be conducted on both the intention-to-treat (ITT) and 'per protocol' cases. Between-treatment or between-group comparisons will be examined using chi-square tests (or Fisher's Exact tests when cell frequencies are small) for categorical outcomes and Student t-tests (alternatively, Wilcoxon Rank Sum Test) for scalar measures. Two-sided statistical tests will be conducted and the significance level will be set at 0.05 for each primary test. The efficacy and safety analyses will be conducted on both the ITT and per protocol population. ITT cases will be all randomized subjects who receive the study medication, while per protocol cases will be randomized subjects who complete the study (including all cause deaths) without any major deviations from the protocol procedures. Descriptive statistics will be used to detail the sample characteristics. Between-treatment arm

differences on key baseline demographic and clinical characteristics will be tested. This latter step will be used to identify potential pre-treatment covariates for subsequent secondary analyses. Key baseline variables include race, gender, length, weight, head circumference, SNAPPE-II score, and gestational age. Descriptive statistics for the total exposure to study drug during the treatment period (number of doses), timing of initial study dose, timing of discontinuation in the event of early termination, and rate of study dropout will be provided. Between-treatment differences will be tested using the statistical methods described earlier. Concomitant medications will be summarized by therapeutic/pharmacological class and treatment group. In addition, they will be listed by treatment group, name of drug, dates administered, dose, frequency and indication.

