Efficacy evaluation: If CC10 is more efficacious than placebo, the CC10 treatment groups will have a higher rate of survival without BPD at 36 weeks CGA and/or survival without CRM at 12 months CGA (we are exploring which of these factors are more accurate predictors of long term respiratory morbidity). A 2 x 2 chi square test will be conducted to examine treatment differences in this binary endpoint and Kaplan-Meier survival curves will be constructed and any differences between the treatments will be tested using a Cox Proportional Hazards Regression Model. Secondly, a logistic regression will be employed to further detail the main and interaction effects of treatment and centers on the primary outcome. Odds Ratios (OR) with 95% confidence intervals (CI) will be provided. Subjects who die from respiratory causes before 12 months CGA will be considered treatment failures in both the ITT and per protocol analyses, and the last observation carried forward (LOCF) imputation method will be applied for early dropouts. For those subjects without diary data at any time point, respiratory status will be estimated based on available data during the follow-up period, including O₂ challenge test, pulmonary questionnaires, and use of asthma medications.

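### Section 8.5 does not name the single test that decides efficacy: its and/or wording conflicts with the one primary endpoint in 8.1, and tests and analysis sets are unranked at 0.05

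*Combined protocol and SAP*

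**What the plan says.** Most of the plan points to one primary question. Section 8.1 states: "The primary outcome of the study will be survival without CRM through 12 months CGA". Section 8.3 lists BPD-free survival at 36 weeks among the secondary, short-term endpoints. The power paragraph of section 8.5 makes placebo against both rhCC10 doses combined the primary analysis, and powers only death or CRM.

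The analysis text in section 8.5 is looser in four places:

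- **Endpoint.** If CC10 works, the treated groups are expected to show a higher rate of "survival without BPD at 36 weeks CGA and/or survival without CRM at 12 months CGA". The next sentence tests a single binary endpoint without saying which of the two it is.
- **Test.** A 2 x 2 chi-square is planned, and in the same sentence Kaplan-Meier curves are added and "any differences between the treatments will be tested using a Cox Proportional Hazards Regression Model". Only the logistic regression that follows is introduced as second in order.
- **Analysis set.** "The efficacy and safety analyses will be conducted on both the ITT and per protocol population". Neither set is named as the main one.
- **Level.** "Two-sided statistical tests will be conducted", and "the significance level will be set at 0.05 for each primary test". The plan gives no hierarchy, alpha split or other multiplicity rule.

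**The concern.** A 5% error rate belongs to one pre-specified test. Here a reader of the results could point to chi-square or Cox, in the ITT or the per-protocol set, and could take the and/or sentence as licence to point to BPD-free survival as well. Nothing in the text settles which result counts if they disagree.

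This matters even in a phase 2 trial. Section 3 gives the purpose as determining efficacy. The introduction to section 8 says that the observed effects will choose the outcome variables and size of a larger study, so a chance finding would be carried forward. BPD would be a weak stand-in: section 2.1 reports that the current BPD definition correctly predicted CRM only 35-40% of the time.

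**Working it through.** **1. The plan's own power figure.** Inputs from section 8.5: 44 v 44 infants, two-sided alpha 0.05, and "Then the proportions with disease or death on placebo and rhCC10 are assumed to have been 0.57 and 0.27". With the pooled-variance two-proportion formula, mean proportion (0.57 + 0.27)/2 = 0.42:

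- SE under no effect = sqrt(2 x 0.42 x 0.58 / 44) = 0.1052
- SE under the alternative = sqrt((0.57 x 0.43 + 0.27 x 0.73) / 44) = 0.1002
- z = (0.30 - 1.96 x 0.1052) / 0.1002 = 0.94, so power = 82.5%

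This reproduces the stated 82%. The exact power of the uncorrected chi-square is 82.6%. The continuity-corrected test (76.1%) and Fisher's exact test (75.7%) do not match. The sample size therefore corresponds to one uncorrected chi-square on all 88 infants.

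**2. Two endpoints, one ITT test each.** If independent, the chance of at least one p<0.05 is 1 - 0.95^2 = 9.75%. For bivariate normal statistics it is 9.5%, 9.1% and 7.8% at test correlations of 0.3, 0.5 and 0.8.

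**3. Simulation under no effect**, 44 v 44, 20,000 trials per scenario. Assumptions not in the documents:

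- death-or-CRM rate 0.42 or 0.57 in both arms
- latent BPD-CRM correlation 0 to 0.8
- per-protocol exclusions of 10-20%, at random
- event times uniform over follow-up

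BPD rates of 0.30, 0.45 and 0.60 lie within the 20-60% quoted in section 2.3. The log-rank test stands in for Cox, as its score test. Cox is applied to CRM only.

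| Route to at least one two-sided p<0.05 | Range over scenarios | One scenario* |
|---|---|---|
| CRM, chi-square, ITT | 4.6-5.2% | 4.7% |
| CRM, chi-square or Cox, ITT | 5.6-6.5% | 6.0% |
| CRM, chi-square, ITT or per protocol | 6.2-7.5% | 7.1% |
| CRM, all four combinations | 7.4-9.2% | 8.6% |
| CRM or BPD, chi-square, ITT | 8.4-10.3% | 8.8% |
| CRM or BPD, all routes | 12.0-15.4% | 14.2% |

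*BPD rate 0.45, death-or-CRM rate 0.57, latent correlation 0.6, 20% excluded.

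**4. What drives the increase.** In the scenario shown, the second analysis set adds 7.06 - 4.74 = 2.3 percentage points and the Cox test adds 6.02 - 4.74 = 1.3. With 10% excluded, the same differences are 6.65 - 4.92 = 1.7 and 6.07 - 4.92 = 1.2. On the named endpoint the choice of set is thus the larger contributor. The choice of test adds less, because the two statistics correlate at about 0.97-0.99. Counting BPD-free survival as a success adds most.

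**5. Direction.** All figures are two-sided. False claims favouring rhCC10 are about half of each, against 2.5% for a single test.

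**The case against.** The strongest defence is that the plan already has a hierarchy and one sentence is loosely worded. The and/or sentence is a hypothesis about what would be seen if the drug works, and its parenthesis says that the trial is exploring which outcome predicts later morbidity better. BPD-free survival is secondary in 8.3, the 0.05 level is for primary tests, and only death or CRM is powered. Chi-square comes first in the efficacy evaluation and is the general method for categorical outcomes. Reporting ITT and per-protocol results side by side is common sensitivity practice. Section 8 is also headed as exploratory.

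Much of this stands. A reader might infer that the plan permits an efficacy claim on BPD-free survival alone, or that the error rate is at least double the nominal 5%. The documents do not support either as stated. No sentence says that one endpoint suffices, and the doubling depends on counting BPD; on the named endpoint the increase is about 1.5 to 1.8 times. Treating all eight combinations of endpoint, test and set as independent would give 1 - 0.95^8 = 33.7%, which is far too high because the tests share the same infants.

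The defence does not supply the missing statement. Being listed first is not being named as decisive, and no section ranks chi-square against Cox or ITT against per protocol. The exploratory heading lowers the stakes, but the same section sizes the trial for a powered test at 0.05.

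**Conclusion.** The concern holds as a conflict of wording plus an unranked choice of test and analysis set; it is not an explicit rule that lets any positive result win. Sections 8.1, 8.3 and the power paragraph define one endpoint and one comparison, and the efficacy evaluation in 8.5 does not follow them.

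The two-sided error rate is about 7-9% on the named endpoint, about 8-10% if BPD-free survival by one ITT test also counts, and about 12-15% over all routes. The simulated ranges depend on the assumptions listed in the working. Per-protocol exclusions in practice would not be random, and the documents state no dropout rate, so the figures indicate scale only. The point should be corrected, but it does not undermine the design.

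**What to change.** In the efficacy evaluation of section 8.5, replace the and/or sentence with:

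> *The efficacy conclusion rests on survival without CRM through 12 months CGA, pooled rhCC10 v placebo, ITT population, chi-square test, two-sided 0.05. BPD-free survival, the Cox model and per-protocol results are secondary or supportive and carry no efficacy claim at 0.05.*

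State that the chi-square is without continuity correction, since that form reproduces the power figure, and refer to the primary test in the singular where the 0.05 level is set. The question of which outcome better predicts later morbidity can stay as a separate exploratory aim.

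The error rate returns to 5% (4.6-5.2% in simulation), and power stays at 82.5% with 44 v 44. The cost is a wording change and no extra infants. The small downside is that BPD, Cox or per-protocol results alone can no longer support an efficacy claim. Making BPD-free survival co-primary with 0.025 for each endpoint would cost more: power for CRM falls to 73.9% (z = (0.30 - 2.241 x 0.1052) / 0.1002 = 0.64).

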4 STUDY DESIGN

This study is designed as a randomized, blinded, placebo-controlled phase 2 trial. The study will enroll premature infants with a gestational age of 24-29 weeks who are receiving positive pressure mechanical ventilation and surfactant replacement therapy for treatment of RDS. Placebo (normal saline) will be compared to two dose groups of rhCC10 as shown in Table 1:

TABLE 1: TREATMENT GROUPS FOR IT RHCC10 ADMINISTRATION

| Treatment | Route of Administration | Number of doses | Intratracheal Dose level |
|------------------|-------------------------|--------------------|--------------------------|
| Placebo (n = 44) | Intratracheal | 1, on day of birth | n/a |
| rhCC10 (n = 22) | Intratracheal | 1, on day of birth | 1.5 mg/kg |
| rhCC10 (n = 22) | Intratracheal | 1, on day of birth | 5 mg/kg |

The clinical study has a blinded, placebo-controlled design. The purpose of blinding the study is to minimize treatment bias while randomization offers each infant the possibility of receiving the study drug.

A total of 88 patients will be enrolled in three treatment groups in which high and low dose rhCC10 will be compared to placebo. A total of 44 patients will receive placebo, 22 patients will receive 1.5 mg/kg rhCC10, and 22 patients will receive 5 mg/kg rhCC10. Complete results of the study should allow direct comparison of three groups.

Patients enrolled in the study will meet the prescribing criteria for *Survanta* or *Curosurf* and will receive the usual recommended clinical dose of surfactant replacement therapy. Each patient will then receive a single IT dose of the study drug (or placebo) within four hours after surfactant. Patients may be given subsequent doses of surfactant if required, but will not receive additional doses of rhCC10.

Concentrations of rhCC10 will be evaluated in serum derived from the infant, umbilical cord, or placental blood before drug administration and in serum or plasma and urine on days 1 and 28, and 12 months CGA. TAF will be obtained on similar days if the infant is still intubated to evaluate the effects of a single IT dose of rhCC10 on native CC10 expression in the lungs. Total protein, TH2 cytokines, IL-6, and cellular infiltrates will also be evaluated in TAF samples, to the extent permitted by the volume of patient samples collected.

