5.3 Randomization

As previously described, two dose levels will be evaluated against the placebo in two consecutive cohorts. The first cohort will randomize patients to receive either 1.5 mg/kg or placebo. The second cohort will randomize patients to receive either 5 mg/kg or placebo. Each cohort will randomize 44 infants to either placebo or drug treatment. The overall design is 2:1:1; 44 (placebo):22 (1.5 mg/kg):22 (5mg/kg). The randomization scheme was developed and is maintained by StudyTrax, a secured electronic data capture platform that is compliant with 21 CFR-11 and HIPAA. A randomization ID is generated when a subject is randomized using the format TMC-001, BWH-002, and

so on (i.e. 3 letter site designation and three numbers designating the sequence in which the patient was enrolled). The randomization scheme uses the permuted block randomization method, with stratification by site and by gestational age group (divided into 24-27 wks CGA and 27-29 wks CGA), with block sizes 2,2,4. For Cohort 1, treatment groups are: Placebo and 1.5 mg/kg. When Cohort 1 is completed, Cohort 2 treatment groups will be: Placebo and 5.0 mg/kg. Cohort is also listed as a Stratification factor so that when Cohort 2 starts, any open blocks from the first cohort will not be filled. The Cohort is automatically set to 1 at the start of the study. Once Cohort 1 is done and Cohort 2 starts, that will change. Each site's pharmacy will receive authorization to access the patient randomization assignment via the Internet on StudyTrax.

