8.4 Secondary Endpoints: Safety and Efficacy - Adverse Events

The safety of the study drug will continue to be assessed by comparing the incidence of adverse events and serious adverse events in the treatment and placebo groups to each other and to the historical incidence of the adverse events at each institution. Safety evaluations will include all serious adverse events up to at least 12 months CGA, and routine laboratory monitoring prior to NICU discharge (CBC, electrolytes, liver function studies, urinalysis, head ultrasound). In addition to evaluating the safety of rhCC10, preliminary efficacy of rhCC10 in this patient population may also be indicated by decreases in the numbers of all SAEs and/or specific types of SAEs (ie. IVH, PVL, ROP, sepsis, infection, etc.).

8.5 Statistical Considerations.

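### Randomisation is stratified by cohort, gestational age and site, but the primary test uses none of them and cohort enters no analysis, so per-dose estimates are open to drift between cohorts

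*Combined protocol and SAP*

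**What the plan says.** Section 5.3 describes permuted blocks with "stratification by site and by gestational age group", and adds a third factor: "Cohort is also listed as a Stratification factor so that when Cohort 2 starts", open blocks from the first cohort are left unfilled. The doses are studied one after the other. "The first cohort will randomize patients to receive either 1.5 mg/kg or placebo"; the second cohort does the same with 5 mg/kg. Each cohort has 44 infants, which with the overall 44:22:22 layout means 22 placebo and 22 active infants per cohort.

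The analysis in section 8.5 uses these factors unevenly:

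- **Primary test**, placebo against both doses combined: "A 2 x 2 chi square test will be conducted to examine treatment differences in this binary endpoint". No stratification factor is used.
- **Site**: only in a secondary logistic regression with treatment and centre.
- **Gestational age**: one of several baseline variables that may become covariates in secondary analyses after between-arm baseline testing. Section 5.3 says imbalance will be considered, but gives no method.
- **Cohort**: in no test, model or covariate list.

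On the doses, section 4 shows placebo as one group of 44 and says: "Complete results of the study should allow direct comparison of three groups". Section 8.5 adds: "Secondarily, the study will yield effect size estimates for each individual dose versus placebo". It does not say which placebo infants are meant. It also justifies having two doses on the ground that "that safety data may facilitate the choice of dose for a future Phase III confirmatory study". Section 8.4 plans the safety assessment by "comparing the incidence of adverse events and serious adverse events in the treatment and placebo groups to each other".

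**The concern.** Two separate issues arise.

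1. **Efficiency of the primary test.** Stratified randomisation balances the arms on factors thought to predict outcome. A test that ignores those factors uses a variance that is too large. It stays valid but becomes conservative to the extent that the strata are prognostic.

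2. **Confounding of dose with calendar period.** Each dose is randomised only against the placebo infants of its own cohort. If all 44 placebo infants serve as the reference, half of them are non-concurrent. Dose against dose is wholly confounded with cohort, for efficacy and for safety. Section 2.6 itself notes that necrotising enterocolitis comes in clusters, so event rates can differ between periods. The safety contrast between doses is also what the plan says may inform the choice of dose for Phase III.

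**Working it through.** **Inputs from the documents.** Event proportions 0.57 (placebo) and 0.27 (rhCC10), 44 against 44, two-sided alpha 0.05 (section 8.5); 22 placebo and 22 active infants per cohort (section 5.3).

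**Assumptions, because the documents give no figures.** Gestational-age log-odds difference of 0 to 2 with a 50:50 split; between-cohort drift D of 0 to 20 points.

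**1. The plan's own power.** The mean proportion is 0.42. Power = Φ{[0.30 − 1.96·√(2·0.42·0.58/44)] / √[(0.57·0.43 + 0.27·0.73)/44]} = Φ[(0.300 − 0.206)/0.100] = 82.5%. Exact enumeration of the uncorrected chi-square gives 82.6%. The stated 82% reproduces.

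**2. Primary test, unstratified against Cochran-Mantel-Haenszel (CMH).** Simulation with 200,000 runs, cohort × gestational-age strata, overall proportions held at 0.57 and 0.27, no cohort effect, site omitted:

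| Log-odds difference | Size, chi-square | Size, CMH | Power, chi-square | Power, CMH |
|---|---|---|---|---|
| 0 | 4.9% | 4.7% | 82.6% | 81.8% |
| 0.5 | 4.8% | 4.8% | 82.8% | 82.6% |
| 1 | 4.2% | 5.0% | 83.1% | 84.5% |
| 1.5 | 3.5% | 5.0% | 84.0% | 87.0% |
| 2 | 2.7% | 4.9% | 84.9% | 89.4% |

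With gestational-age splits of 68:32 and 32:68, the power forgone at log-odds 2 is 4.3 and 3.7 points.

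A second simulation (6,000 runs, two sites assumed) gave site, gestational age and cohort odds ratios of 2, 3 and 2, then 4, 6 and 4. CMH over all three factors gained about 4 points (73.7% to 77.4%) and 12 points (58.7% to 71.1%). Those power levels should not be set against 82%: the within-stratum odds ratio was held fixed, so the overall risk difference shrank to about 27 and 23 points.

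In the null runs of that second simulation the mean pooled difference was 0.000 to 0.001 with cohort effects present. Drift therefore does not bias the primary comparison.

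**3. Each dose against placebo, no drug effect.** Let the underlying rates in the two cohorts be 0.57 ± D/2. The mean rate over all 44 placebo infants is 0.57, so the expected difference for a dose is (0.57 ± D/2) − 0.57 = ±D/2, with opposite signs for the two doses. Exact type I error of the uncorrected chi-square:

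| Drift D | Bias against all 44 | Dose vs all 44 | Dose vs concurrent 22 | Dose vs dose |
|---|---|---|---|---|
| 0 | 0 | 4.7% | 4.8% | 4.8% |
| 5 points | 2.5 points | 5.0-5.2% | 4.7-4.8% | 6.0% |
| 10 points | 5 points | 6.1-6.5% | 4.6-4.9% | 9.9% |
| 20 points | 10 points | 11.0-11.3% | 4.7-4.9% | 26.2% |

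Ranges cover which of the two cohorts the dose is in.

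**4. Price of the concurrent reference.** Exact power at 0.57 against 0.27 is 63.6% for 22 against 44 and 52.4% for 22 against 22. The 95% confidence interval half-width is 1.96·√(0.27·0.73/22 + 0.57·0.43/n) = 0.236 for n = 44 and 0.278 for n = 22.

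**The case against.** The strongest reply has four parts.

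- **The chi-square is not wrong.** It is valid and never falls below the planned power in the first simulation. CMH helps only if gestational age is fairly strongly prognostic, and the documents give no figure for that. This stands, and it is why the primary part is an improvement rather than an error. The improvement costs at most 0.8 points in the scenarios examined and matches the analysis to the randomisation.
- **The per-dose harm depends on a reading.** Section 5.3 could be taken to mean concurrent placebo, and then type I error stays near 5%. That is fair: the defect is an unstated reference group. But the single placebo group of 44 in section 4 points towards pooling, and no reading rescues dose versus dose.
- **These are exploratory, secondary estimates and the drift is assumed.** Also true. At 5 points of drift the effect is negligible, and clustering of enterocolitis is only indirect evidence about 12-month respiratory morbidity. However, section 8 says the observed effects will be used to choose outcomes and size the next trial.
- **Pooling may estimate better.** At 10 points of drift the root mean squared error is 0.126-0.139 with all 44 placebo infants and 0.138-0.151 with 22 concurrent ones; pooling is better up to about 14 to 15 points. This stands. The choice of reference is a trade between bias and variance, which is a reason to keep the pooled estimate as supportive and to fix the choice in advance.

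**Conclusion.** The point holds and should be addressed; it does not overturn the primary analysis. The pooled comparison is unbiased and its 82% power is correct. Ignoring the strata forgoes about 1 to 4.5 points of power if the gestational-age log-odds difference is 1 to 2, and nothing at 0.5 or below.

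The more consequential gap concerns the doses. Without a cohort term or a stated concurrent reference, each per-dose estimate may carry half of any between-cohort drift, and the dose contrast that section 4 presents as direct carries all of it. Confidence in the size is moderate, because stratum effects and drift are assumed. The structure of the problem follows from the design alone.

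**What to change.** Before unblinding, amend sections 4 and 8.5 as follows.

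1. Make the primary test CMH (or logistic regression) stratified by cohort and gestational-age group as recorded at randomisation. This gives four strata averaging 88/4 = 22 infants. Keep the planned centre model as support, since adding site would thin the strata. Section 5.3 places week 27 in both gestational-age groups, so the boundary needs to be stated.
2. Define each per-dose estimate as the dose against its own cohort's 22 placebo infants. A model on all 88 infants with cohort and two dose terms gives the same unadjusted estimate.
3. Label any estimate against all 44 placebo infants without a cohort term as supportive and partly non-concurrent.
4. Replace the promise of a direct three-group comparison with each dose against concurrent placebo, and state that dose versus dose is descriptive for both efficacy and safety.
5. Adjust for the pre-specified stratification factors rather than for covariates selected by baseline testing.

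The cost is wording only, with no change to randomisation or data collection. Primary power falls from 82.6% to 81.8% if the strata carry no prognostic information. Per-dose power falls from about 64% to 52%, and the confidence interval half-width widens from about 24 to 28 points, for secondary estimates only.

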6.9 Concomitant Medications

No other investigational drugs may be administered to patients enrolled in the study. Medications that may be indicated as part of standard care for this group of patients will be administered as needed. Postnatal corticosteroids (other than hydrocortisone utilized for the treatment of early hypotension/adrenal insufficiency) will be avoided, except in cases in which the attending physician determines that the infant's life would be jeopardized without their use. The MOO will include a recommended protocol for postnatal corticosteroid treatment for severe respiratory failure if the clinician feels this therapy is warranted.

Other medications that have a small, but significant impact on the incidence of BPD include Vitamin A and caffeine. Vitamin A is not used in either clinical site and caffeine is administered to all infants within the first 48-72 hours of life (will be seen equally in rhCC10 and placebo treated infants). The impact of all medications will be examined in the final statistical analysis.

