8 EXPLORATORY ENDPOINTS

Several measures of efficacy in reducing respiratory morbidity in the short and long term will be explored. The trends and effects observed in this study will be used to determine appropriate efficacy outcome variables and the numbers of infants that would be required to be enrolled in a larger Phase 2 or Phase 3 study.

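### The plan promises odds ratios with 95% confidence intervals but does not say which treatment odds ratio is the trial's estimate, and it plans no interval on the risk scale used to size the trial.

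*Combined protocol and SAP*

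**What the plan says.** The efficacy evaluation in section 8.5 names three analyses of the primary endpoint.

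- A 2 x 2 chi-square test. No estimate or interval is attached to it.
- Kaplan-Meier curves with a Cox model, described as a way of testing the difference. No hazard ratio or interval is named.
- As a second step, a model: "a logistic regression will be employed to further detail the main and interaction effects of treatment and centers on the primary outcome".

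The sentence after the model reads "Odds Ratios (OR) with 95% confidence intervals (CI) will be provided". It is the only mention of a confidence interval in the documents. The section does not say whether these odds ratios come from the interaction model, from a main-effects model or from the 2 x 2 table. It gives no coding for centre, no rule for dropping the interaction and no way of combining centre-specific odds ratios.

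Section 5.3 stratifies the randomisation by site and gestational age group, and lists cohort as a further stratification factor. Of these, only centre is in the model.

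Section 8 says that what is observed will be used to settle the outcome variables and "the numbers of infants that would be required to be enrolled in a larger Phase 2 or Phase 3 study".

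**The concern.** If the next study is to be sized from this one, the size of the effect and its uncertainty are a main product of the trial. A logistic model with treatment, centre and their product does not have a single treatment effect. What its treatment coefficient means depends on how centre is coded, and the plan leaves that open. Under reference-cell coding, a common default, the coefficient is the effect in one centre and rests on that centre's infants only. Under sum-to-zero coding it is the unweighted mean of the centre log odds ratios. An analyst could follow the plan to the letter and report either, and the choice could be made after the data are seen.

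Two further gaps affect the same estimate. The model omits two of the factors on which the trial randomises. And the trial was sized on two proportions, yet no interval for their difference is planned.

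**Working it through.** **Inputs.** All are from section 8.5 unless stated.

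- Failure rates: "Then the proportions with disease or death on placebo and rhCC10 are assumed to have been 0.57 and 0.27".
- Size and power: "with 44 subjects on placebo and 44 subjects in the two dose groups combined, power will be 82" per cent.
- Test: "Two-sided statistical tests will be conducted and the significance level will be set at 0.05 for each primary test".
- Allocation: "randomized to placebo, lower dose, or higher dose rhCC10 with an allocation ratio of 2:1:1", which is 1:1 once the doses are pooled.
- Number of centres: not stated outright. Section 6.9 says "Vitamin A is not used in either clinical site", which implies two. Two equal centres is therefore an assumption; three and four are shown as a range.

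**1. The plan's own figure.** The pooled rate is 0.42. The standard error is sqrt(2 × 0.42 × 0.58/44) = 0.1052 under the null and sqrt((0.57 × 0.43 + 0.27 × 0.73)/44) = 0.1002 under the alternative. Power = Φ((0.30 − 1.96 × 0.1052)/0.1002) = 82.5%. The stated 82% reproduces.

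**2. Whole-trial odds ratio of failure, rhCC10 against placebo.** Log OR = ln[(0.27/0.73)/(0.57/0.43)] = −1.276, so OR = 0.279. SE = sqrt(1/(44 × 0.57 × 0.43) + 1/(44 × 0.27 × 0.73)) = 0.456. The 95% CI is 0.11 to 0.68.

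**3. Interaction model, same rates in every centre.** Under reference-cell coding only the reference centre's infants count:

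| Equal centres (assumed) | Infants per arm in reference centre | SE of log OR | 95% CI for OR |
|---|---|---|---|
| 2 | 22 | 0.645 | 0.08 to 0.99 |
| 3 | 14.7 | 0.790 | 0.06 to 1.31 |
| 4 | 11 | 0.912 | 0.05 to 1.67 |

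Under sum-to-zero coding with two equal centres, SE = ½ × sqrt(0.645² + 0.645²) = 0.456, the whole-trial value.

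**4. Wald power of the treatment coefficient,** Φ(1.276/SE − 1.96). It is 80% for the whole-trial log OR. Conditional on reference-cell coding and the assumed centre sizes, it is 51% with two equal centres, and 33% if the reference centre holds 30% of infants (13.2 per arm, SE 0.833).

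**5. One dataset, several answers.** This is an invented split: failures of 14/22 on placebo against 4/22 on rhCC10 in centre A, and 11/22 against 8/22 in centre B. The totals are 25/44 and 12/44, close to the planned rates.

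| Model | Treatment OR | 95% CI |
|---|---|---|
| Interaction, A as reference | 0.127 | 0.032 to 0.509 |
| Interaction, B as reference | 0.571 | 0.171 to 1.908 |
| Interaction, sum-to-zero | 0.269 | 0.107 to 0.676 |
| Main effects, treatment and centre | 0.285 | 0.117 to 0.695 |
| Unadjusted 2 x 2 table | 0.285 | 0.117 to 0.696 |

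The first three rows are the same fitted model. Only the coding differs.

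**6. Risk scale.** At the planned rates the risk difference is 0.57 − 0.27 = 0.30, with 95% CI 0.30 ± 1.96 × 0.1002, or 0.10 to 0.50. The ratio of failure risks, placebo to rhCC10, is 0.57/0.27 = 2.11, while the odds ratio in the same direction is 1/0.279 = 3.58.

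**7. Can the data carry a main-effects model?** Expected failures are 44 × 0.57 + 44 × 0.27 = 37. With two centres, the model with treatment, centre, gestational age group and cohort has four coefficients besides the intercept, or about nine failures for each.

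**The case against.** A reader might infer that the reported odds ratio will describe one centre and not the trial. The documents do not support that as a fact. It needs both reference-cell coding and an interaction kept in the model, and section 8.5 states no coding. A main effect beside an interaction is often understood as an average over centres. Nor is the odds-ratio sentence tied expressly to the interaction model: a ratio from the 2 x 2 table would satisfy it.

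A reader might also infer a loss of power from the 51% and 33%. That does not follow either. The primary test is the chi-square of placebo against the combined doses, and its power reproduces. The lower figures belong to a coefficient that the plan never names as its efficacy test.

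A third inference would be that empty cells make the model impossible to fit. With two centres of 22 per arm, the chance of no failures in a given rhCC10 cell is 0.73^22, about 0.1%, so this is not a practical worry.

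It can also be said that arm-level summaries are planned, that effect sizes for each dose are promised, that a risk difference can be computed from the table, and that the endpoints are headed exploratory. All of that stands. It does not settle which treatment odds ratio is the trial's estimate, and a difference that could be computed later is not a planned interval.

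**Conclusion.** The point holds as a gap in the definition of the estimate. The plan's only confidence intervals are for odds ratios introduced straight after an interaction model, and the treatment odds ratio meant as the trial's result is not identified. With two equal centres and equal effects in both, the choice of coding moves the standard error of the log odds ratio between 0.456 and 0.645. Where the centres differ, it moves the estimate too, as the invented split shows. The model also leaves out gestational age group and cohort, and no interval is planned for the risk difference. The number and size of centres are assumptions, and the figures scale with them. The primary test and its power are untouched. This is a free improvement to the plan, not a fault in the primary analysis.

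**What to change.** State in section 8.5 that the trial's treatment effect (combined doses against placebo) is estimated from a main-effects logistic model with treatment, centre, gestational age group as randomised, and cohort. Report from that model the odds ratio with its 95% CI, and a risk difference standardised over the analysed infants with its 95% CI. Name the interval method for the latter, for example the delta method. The standardised difference is on the scale of the sizing assumption and of the arm proportions that the chi-square compares. The adjusted odds ratio is conditional on the covariates and need not equal the one from the 2 x 2 table, so say which is which.

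Fit the treatment-by-centre interaction in a separate model, labelled as a description of heterogeneity, and list failure counts by centre and arm beside it. Keep the chi-square as the primary test.

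The cost is a few sentences in the analysis plan, fixed before unblinding. It needs no extra patients, data or procedures.
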